12.1.1.2. Serious Adverse Event

A SAE is an AE/reaction that results in any of the following outcomes:

- Death
- Is life-threatening (subject is at immediate risk of death at the time of the event; it does not refer to an event that hypothetically might have caused death if it were more severe)
- Requires subject hospitalization (formal admission to a hospital for medical reasons) or prolongation of existing hospitalization
- Results in persistent or significant disability/incapacity (i.e., there is a substantial disruption of a person's ability to carry out normal life functions)
- Is a congenital anomaly/birth defect

Important medical events that may not result in death, are not life-threatening, or do not require hospitalization may be considered a SAE when, based upon appropriate medical judgment, they may jeopardize the subject's health or may require medical or surgical intervention to prevent one of the outcomes listed in this definition. For this study, examples of such events may include allergic bronchospasm requiring intensive treatment in an emergency room or at home, blood dyscrasias, or convulsions that do not result in subject hospitalization.

In addition, the Sponsor considers events of abortion (spontaneous or induced), fetal demise, and still birth as SAEs for reporting purposes.

Some hospitalization scenarios, as outlined in Section 12.1.1.1 do not require reporting as SAEs.

Overdose will be considered an SAE only if any of the seriousness criteria are met. Any clinical complication in association with the overdose should be reported as an AE or SAE (as applicable) along with the overdose (see Section 12.2.2). Details of signs or symptoms, clinical management and outcome should be reported, if available. Overdose without associated signs or symptoms should not be recorded as AEs but should be recorded as protocol deviations.

12.1.1.3. Adverse Events of Special Interest

For this protocol, non-serious treatment-emergent maculopapular rashes that are deemed related to BCX7353 will be considered EOSIs. This does not include other types of rashes such as urticaria or eczema. All treatment-emergent skin conditions should be reported as AEs but only maculopapular rashes deemed related to BCX7353 should be considered EOSIs.

An EOSI event in and of itself will not be considered serious unless it meets the seriousness criteria above. Events of maculopapular rash assessed as possibly, probably, or definitely related to BCX7353 regardless of severity must be reported to the Sponsor Medical Monitor as described in Section 12.1.5.1. Management of BCX7353 drug-related rash is provided in Section 11.1.12.

12.1.2. Method, Frequency, and Time Period for Detecting Adverse Events and Reporting Serious Adverse Events

Reports of all AEs and SAEs, regardless of Investigator attribution, are to be collected from the time of signing of the informed consent through to the last study visit (i.e., through the posttreatment end-of-study visit). All AEs and SAEs are to be reported on the AE CRF.

AEs should be documented on CRFs as Investigators become aware of them. AEs are to be followed until the event resolves. If an event is ongoing at the End of Study visit, Grade 1 and 2 events do not need to be followed if the event is deemed unlikely to be related or not related to study drug (see Section 12.1.3 for AE grading). For all Grade 3 and 4 events or events deemed at least possibly related to use of study drug, the event should be followed until the AE is resolved or the subject is in a clinically stable condition with regards to the AE.

The Investigator shall report all SAEs immediately to the Sponsor by communicating with the Medical Monitor (phone or email) and by submission of an SAE report form via email, and entering the event onto the AE CRF within 24 hours of their knowledge of the event (see Section 12.1.5). The SAE report form is a detailed, written report on the SAE provided by the Sponsor or designee. The Investigator should follow all unresolved SAEs observed during the

study until they are resolved, or are judged medically stable, or are otherwise medically explained.

The Investigator should attempt, if possible, to establish a diagnosis based on the presenting signs and symptoms. In such cases, the diagnosis should be documented as the AE and not the individual sign/symptom. If a clear diagnosis cannot be established, each sign and symptom must be recorded individually. Once a diagnosis is made during evaluation or treatment, the Investigator will update the AE record with this diagnosis. The immediate and follow-up reports shall identify subjects by the unique subject numbers assigned to them to ensure that the Sponsor shall have the necessary information to continuously assess the benefit-risk profile of the study drug in clinical trial.

12.1.3. Definition of Severity

All AEs will be assessed (graded) for severity and classified using the DMID criteria for grading AEs (Publish date November 2007, see Section 16.1). Any AEs not covered by the DMID criteria will be assessed and classified into 1 of 4 clearly defined categories as follows:

- Mild:** (Grade 1): Transient or mild symptoms; no limitation in activity; no intervention required. The AE does not interfere with the participant's normal functioning level. It may be an annoyance.
- Moderate:** (Grade 2): Symptom results in mild to moderate limitation in activity; no or minimal intervention required. The AE produces some impairment of functioning, but it is not hazardous to health. It is uncomfortable or an embarrassment.
- Severe:** (Grade 3): Symptom results in significant limitation in activity; medical intervention may be required. The AE produces significant impairment of functioning or incapacitation.
- Life-threatening:** (Grade 4): Extreme limitation in activity, significant assistance required; significant medical intervention/therapy required to prevent death, hospitalization or hospice care probable.

Severity refers to the medical perspective of an event while seriousness reflects the outcome of the event (i.e., hospitalization). Events of mild severity can lead to hospitalization and therefore be serious while severe events such as a headache may not meet seriousness criteria.

12.1.4. Definition of Relationship to Study Drug

The Investigator or medically qualified designee must review each AE and make the determination of relationship to study drug using the following guidelines:

- Not Related:** The event can be readily explained by other factors such as the subject's underlying medical condition, concomitant therapy, or accident, and no temporal relationship exists between the study drug and the event.

Unlikely:	The event does not follow a reasonable temporal sequence from drug administration and is readily explained by the subject's clinical state or by other modes of therapy administered to the subject.
Possibly Related:	There is some temporal relationship between the event and the administration of the study drug and the event is unlikely to be explained by the subject's medical condition, other therapies, or accident.
Probably Related:	The event follows a reasonable temporal sequence from drug administration, abates upon discontinuation of the drug, and cannot be reasonably explained by the known characteristics of the subject's clinical state.
Definitely Related:	The event follows a reasonable temporal sequence from study drug administration, follows a known or suspected response pattern to the study drug, is confirmed by improvement upon stopping the study drug (dechallenge), and reappears upon repeated exposure (rechallenge, if rechallenge is medically appropriate).

The Sponsor may upgrade causality if deemed appropriate.

12.1.5. Reporting Serious Adverse Events and Suspected Unexpected Serious Adverse Reactions

Any SAE must be reported by phone or email to the Sponsor Medical Monitor and in writing via email using the SAE report form within 24 hours of the Investigator's awareness of the SAE. In addition, all SAEs must be recorded on the AE CRF in real time. All additional follow-up evaluations of the SAE must be reported to BioCryst or its designee as soon as they are available. The SAE report forms should be sent to the following email address:

Phone (24 hours) [contact]

Email: [contact]

Immediate reporting should allow BioCryst to take the appropriate measures to address potential new risks in a clinical trial. Therefore, the initial report should be submitted by the Investigator within a very short period of time and under no circumstances should this period exceed 24 hours following awareness of the SAE.

The follow-up report should allow BioCryst to determine whether the SAE requires a reassessment of the benefit-risk profile of the study drug in clinical trial, if the relevant information was not already available and provided in the initial report.

US-based Investigators or designees at each site are responsible for submitting any investigational new drug (IND) safety report (initial and follow-up) (i.e., suspected unexpected serious adverse reactions [SUSARs]) or other safety information (eg, revised IB) to the IRB and for retaining a copy in their files, unless otherwise instructed.

European-based Investigators or designees at each site are responsible for retaining copies of all SUSAR reports (initial and follow-up) and other safety information (eg, revised IB) in their files.

BioCryst or its designee will submit all SUSAR reports (initial and follow-up) or other safety information (eg, revised IB) to the required authorities.

BioCryst shall ensure that all relevant information about SUSARs that are fatal or life-threatening is recorded and reported as soon as possible to the competent authorities in all European Member States concerned, the US, and other countries as warranted as well as to the independent ethics committees (IECs), and in any case no later than seven (7) days after knowledge by BioCryst of such a case, and that relevant follow-up information is subsequently communicated within an additional eight (8) days. All other SUSARs shall be reported to the competent authorities concerned and to the IECs concerned as soon as possible but within a maximum of 15 days of first knowledge by BioCryst. BioCryst or designee shall also inform all Investigators.

12.1.5.1. Reporting Events of Special Interest

Although not an SAE, all events of diffuse maculopapular rash assessed as related to BCX7353 regardless of severity, must be reported to the Sponsor Medical Monitor in writing via email using the SAE/EOSI report form after the Investigator's assessment of the event. High resolution photographs must also be submitted as described in Section 11.1.12. In addition, the event must be recorded on the AE CRF in real time. All additional follow-up evaluations of the event must be reported to BioCryst or its designee as soon as they are available. The SAE/EOSI report form should be sent to the following email address:

Phone (24 hours) [contact]

Email: [contact]

This method of reporting will allow BioCryst to obtain more information than can be captured in the eCRF for this event. The report form will allow a full clinical description and information regarding the evaluation that cannot be documented in the EDC due to free text limitations to be shared with BioCryst. Therefore, the initial report and photographs should be submitted by the Investigator within a very short period of time.

The follow-up report should contain new information about the clinical course, medical evaluation, additional photographs (if relevant), biopsy (if done), and laboratory results (if done).

12.1.6. Pregnancy

Any female subject who becomes pregnant during the course of the study should have study drug discontinued immediately and must be followed through the end of the pregnancy. Male subjects whose partners become pregnant do not need to discontinue study drug. While pregnancy is not considered an AE, all cases of fetal drug exposure via the parent as a study participant (including partners of study participants) are to be reported immediately to BioCryst or its designee.

Consent from pregnant partners of study participants will be obtained prior to reporting any details of the pregnancy. Information related to the pregnancy must be given on a "Pregnancy Confirmation and Outcome" form that will be provided by the Sponsor or its designee so that the pregnancy may be followed and an outcome determined. Any AEs or SAEs experienced by a pregnant subject are to be reported as directed above in Section 12.1.2 and Section 12.1.5. Any complications reported in a subject's pregnant partner should be reported on the Pregnancy Confirmation and Outcome form. All pregnancies must be followed to outcome which occurs

when an infant is delivered (live or still born), there is fetal demise, or there is an abortion (spontaneous or induced). Abortion (spontaneous or induced), fetal demise, and still birth along with congenital abnormalities in the newborn, should be reported as separate SAEs.

12.1.7. Serious Breaches of Good Clinical Practice

It is the responsibility of the Sponsor to notify the licensing authority of any serious breach of Good Clinical Practice (GCP) which is likely to effect, to a significant degree, the safety or mental integrity of the subjects of the study or the scientific value of the study. All serious breaches will be notified to the relevant competent authority within 7 days. The reporting to the Sponsor will be performed by the party who suspects the serious breach.

12.1.8. Treatment Interruptions

Treatment interruptions as a result of Investigator management of AEs potentially related to study drug are permissible. Resumption of study drug administration is also permissible upon resolution of the event, as assessed by the Investigator, with a plan for stringent monitoring of the subject for recurrence of the AE as appropriate. In addition, other extenuating circumstances may lead to treatment interruptions such as vomiting during an abdominal HAE attack or required fasting for medical procedures; in these cases, study drug should be resumed once the extenuating circumstance is resolved.

The Sponsor Medical Monitor should be notified in the event of a treatment interruption due to an AE. Any treatment interruption will be recorded in the CRF and source documents, including the reason for the interruption.

12.2. Toxicity Management

The Investigator (or qualified designee) will grade clinically significant events and laboratory abnormalities according to that detailed in Section 12.1.3. Grade 3 and 4 clinically significant laboratory abnormalities should be confirmed by repeat testing and before any contemplated study drug discontinuation, unless such a delay is not consistent with good medical practice.

In the event that a new safety signal emerges, a meeting of the DMC may be convened by the Sponsor to evaluate risk to subjects and recommend appropriate actions. Based on the data presented, a decision will be made as to whether to halt the study, to continue dosing, or to continue dosing with provisions introduced into the protocol via substantial amendment.

12.2.1. Rash

Special evaluation of BCX7353 related maculopapular drug rash is required as per Section 11.1.12 and special reporting is described in Section 12.1.5.1.

Management of rash should be based on best medical practice and address the subject's presentation. If a subject experiences a Grade 3 or 4 rash suspected to be due to BCX7353, the subject should have BCX7353 dosing stopped immediately as per Section 8.3.2. Grade 3 rashes would include rashes with vesiculation, moist desquamation, or ulceration and Grade 4 rashes would encompass rashes with mucous membrane involvement or significant exfoliation, erythema multiforme, suspected Stevens-Johnson syndrome, or necrosis requiring surgery.

12.2.1.1. Study Drug Administration for Grade 1 or 2 Rashes Considered Related to Study Drug

Investigators and subjects may elect to continue dosing if the subject experiences a Grade 1 or 2 rash that is deemed related to BCX7353 but the subject is considered to be deriving benefit. By DMID criteria, this reaction would be described as pruritus and/or erythema (Grade 1) or a diffuse maculopapular rash and/or dry desquamation (Grade 2). In addition, subjects would have to be constitutionally well (no fever, no change in appetite, no malaise, etc.), have no mucosal involvement, no vesicles and have no evidence of any hypersensitivity involving the liver or kidney. If laboratory assessment is performed mild or moderate eosinophilia may be present but should not prevent continuation of study drug if all other criteria are met. Rash treatment should primarily address symptoms (i.e., antihistamines, topical antipruritics and/or topical corticosteroids). Oral corticosteroids should be avoided, as there is no evidence that oral corticosteroids benefit patients with bland drug-related cutaneous reactions.

If the subject's rash does not improve, or worsens to include vesicles, wet desquamation or ulceration (Grade 3), then BCX7353 should be immediately discontinued. Subjects who remain on study drug should be followed closely until the rash resolves.

12.2.2. Aminotransferase (ALT or AST) Elevation

All baseline or treatment-emergent ALT or AST elevations $> 3 \times \text{ULN}$ (ie, Grade 3 and above) should be confirmed within 72 hours with repeat assessment of ALT and AST as well as total bilirubin, ALP, prothrombin time /INR, and complete blood count for eosinophil levels. If subjects are asymptomatic with no other pertinent laboratory abnormality, study drug may be continued under close observation with every 2 week assessment of transaminase levels, total bilirubin, and ALP. These may be done at a local laboratory as long as results are reported to the Investigator as soon as they are available and the investigative site contacts the subject to ascertain any symptoms. If either ALT or AST continue to increase and the subject remains asymptomatic, study drug dosing must be held if:

- Either ALT or AST is $> 5 \times \text{ULN}$ for more than 2 weeks
- The ALT or AST reaches $> 8 \times \text{ULN}$

The subject should continue regular assessments as deemed appropriate by the Investigator of ALT, AST, total bilirubin, ALP, prothrombin time/INR, and complete blood count for eosinophil levels until ALT and/or AST are $< 3 \times \text{ULN}$.

Provided specific criteria are met, the Investigator and subject may elect to resume BCX7353 dosing. All of the following criteria must be met for dosing to resume:

- The subject is considered to have been deriving benefit from BCX7353 prior to holding study drug.
- Transaminases return to $\leq 2 \times \text{ULN}$ for subjects whose baseline transaminase levels were above the ULN, and $\leq \text{ULN}$ for those whose baseline transaminase levels were $\leq \text{ULN}$.
- Subjects have not initiated or restarted androgens during the period BCX7353 was held.
- The subject agrees to continue every 2 week monitoring of ALT, AST, total bilirubin, ALP, CBC (eosinophil levels) and prothrombin/INR until levels appear stable and

transaminase levels remain $< 3 \times \text{ULN}$ for at least 1 month after restarting BCX7353 dosing.

If at any time, the criteria as outlined in Section 8.3.2 is met, the study drug must be permanently discontinued.

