8.3.2. Subject Discontinuation from Study Drug

A subject will be permanently withdrawn from study drug for any of the following bulleted reasons, which will be recorded in the source documents and CRF. When medically feasible, the Medical Monitor must be consulted prior to subject discontinuation. In all cases, subjects who prematurely and permanently discontinue study drug should complete all scheduled procedures for the end-of-study visit outlined in Table 3.

- Emergence of any laboratory abnormality or AE that in the judgment of the Investigator compromises the ability of the subject to continue study-specific procedures or it is considered not to be in the subject's best interest due to an altered benefit-risk profile
- Reoccurrence of treatment-emergent AST or ALT elevation $> 5 \times \text{ULN}$ (confirmed) if BCX7353 is restarted after meeting hold criteria as outlined in Section 12.2.2.
- Treatment-emergent ALT or AST $> 3 \times \text{ULN}$ combined with either laboratory abnormalities indicative of significant hepatic toxicity (ie, meeting Hy's law, total bilirubin $> 2 \times \text{ULN}$ OR with an INR > 1.5) or with symptomatology of acute hepatitis (ie, severe fatigue, nausea, vomiting, right upper quadrant pain and tenderness, fever, rash, and/or eosinophilia [$> 5\%$])
- Subsequent determination that inclusion/exclusion criteria were not met
- Intercurrent illness or emergence of a new illness/medical condition that would, in the judgment of the Investigator, affect assessments of clinical status to a significant degree
- Subject noncompliance with study drug or to the protocol
- Subjects with BCX7353-related Grade 3 or 4 rash as described by the Division of Microbiology and Infectious Diseases (DMID) criteria "skin-mucocutaneous" will be discontinued from study, if suspected to be due to BCX7353, and treated according to best medical practice. All subjects with a suspected drug rash should undergo specific rash evaluation as described in Section 11.1.12. A Grade 3 rash is defined as vesiculation or moist desquamation or ulceration, and a Grade 4 rash is defined as exfoliative dermatitis, mucous membrane involvement or erythema multiforme or

suspected SJS or necrosis requiring surgery. Subjects with a Grade 1 or 2 study drug-related rash may continue BCX7353 if the Investigator and subject deem it appropriate.

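### Subjects kept on BCX7353 with ALT or AST above 3 × ULN have no clearly scheduled PT/INR after the 72-hour confirmation, so the INR > 1.5 stop could be recognised late

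*Protocol*

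**What the plan says.** Protocol Section 8.3.2 lists the grounds for permanent withdrawal from study drug. One is treatment-emergent ALT or AST above 3 × ULN combined with total bilirubin above 2 × ULN, "OR with an INR > 1.5) or with symptomatology of acute hepatitis". Section 12.2.2 makes this a standing rule: "If at any time, the criteria as outlined in Section 8.3.2 is met, the study drug must be permanently discontinued".

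Section 12.2.2 then sets the testing in four steps.

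- **Confirmation.** "All baseline or treatment-emergent ALT or AST elevations" above 3 × ULN "should be confirmed within 72 hours with repeat assessment of ALT and AST as well as total bilirubin, ALP, prothrombin time /INR", and a blood count for eosinophils.
- **Continued dosing.** If the subject has no symptoms and no other relevant laboratory finding, "study drug may be continued under close observation with every 2 week assessment of transaminase levels, total bilirubin, and ALP".
- **After the hold rules.** "The subject should continue regular assessments as deemed appropriate by the Investigator of ALT, AST, total bilirubin, ALP, prothrombin time/INR, and complete blood count", until ALT and/or AST fall below 3 × ULN. No interval is given.
- **Restart after a hold.** "The subject agrees to continue every 2 week monitoring of ALT, AST, total bilirubin, ALP, CBC (eosinophil levels) and prothrombin/INR", until values are stable and transaminases have stayed below 3 × ULN for at least a month.

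The hold rules apply to an asymptomatic subject whose values keep rising. Dosing is held if ALT or AST stays above 5 × ULN for more than 2 weeks, or reaches more than 8 × ULN.

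**The concern.** The 8.3.2 rule has a bilirubin arm and an INR arm. For a subject who stays on drug, bilirubin is on the two-weekly list and INR is not. Half of a mandatory laboratory stop therefore has no clear schedule behind it during the period when the subject is still being dosed with raised transaminases.

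Section 5.7 names transaminase elevation as one of two important potential risks. Section 14.4 says that, apart from Section 8.3, no other formal stopping rules are defined for individual subjects. A subject could meet the INR criterion while dosing, and the site would learn of it only when the Investigator chose to test or at the next visit. No endpoint or analysis is affected. What is at stake is prompt application of a safety rule that the protocol already contains.

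**Working it through.** The plan states no figure for this interval, so there is none to reproduce. The check compares the text of the two sections and then does date arithmetic.

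**Step 1: which tests are fixed at each stage of 12.2.2**

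| Stage | ALT/AST, bilirubin, ALP | PT/INR |
|---|---|---|
| Confirmation | within 72 hours | within 72 hours |
| Continued dosing above 3 × ULN | every 2 weeks | not listed |
| Regular-assessments sentence | at Investigator discretion | at Investigator discretion |
| After a restart | every 2 weeks | every 2 weeks |

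PT/INR is therefore not absent between confirmation and the next visit, but nothing clearly fixes when it is drawn. The regular-assessments sentence comes straight after the hold rules and does not say whether it covers held subjects, continuing subjects or both.

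**Step 2: whether the hold rules close the gap**

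A subject who stays between 3 and 5 × ULN is not above 5 × ULN and has not reached 8 × ULN, so neither hold rule applies. That subject may continue dosing on the two-weekly list.

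**Step 3: the longest wait for the next visit-based PT/INR**

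Inputs: visit days 29 (± 2) and 85 (± 2), then 169, 337, 505 and 673 (each ± 6), from Protocol Sections 10.3.3 and 10.3.4. The elevation is taken to be found at a visit and confirmed 3 days later.

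Nominal wait = next visit day − visit day − 3. The maximum adds both visit windows.

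- Week 4 to 12: 85 − 29 − 3 = 53 days; maximum 53 + 2 + 2 = 57.
- Week 12 to 24: 169 − 85 − 3 = 81 days; maximum 81 + 2 + 6 = 89.
- Week 24 to 48: 337 − 169 − 3 = 165 days; maximum 165 + 6 + 6 = 177. Weeks 48 to 72 (505 − 337) and 72 to 96 (673 − 505) have the same spacing.

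Two-weekly panels falling strictly before the next visit in a 24-week interval: 164/14, rounded down, is 11 nominally; 176/14, rounded down, is 12 at the maximum. These panels could all pass with no PT/INR required on a fixed schedule.

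These are ceilings. They need an elevation that persists for the whole interval, and Section 5.7 describes the increases as generally transient. They also assume that each visit includes the coagulation panel. The grid of Protocol Table 3 is not readable in the available text. Section 7 lists coagulation among the laboratory assessments made at study visits, and the schedule in SAP Table 3, written for an earlier protocol version, pairs it with chemistry and hematology.

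**Step 4: how many subjects**

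Section 5.2.2 reports 13 subjects with treatment-emergent Grade 3 or 4 ALT. All but 1, so 13 − 1 = 12, stopped androgens 7 to 9 days from first dose. The 28-day rule in Section 8.2.2 now bars that pattern. The remaining subject stopped less than 2 months from first dose and may or may not be barred. No interim subject had synthetic dysfunction.

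**The case against.** The strongest reply is that Section 12.2.2 already covers this. Its confirmation rule speaks of all elevations above 3 × ULN. On that wording, every two-weekly result above the threshold would trigger a new 72-hour panel with PT/INR. A short surveillance panel, backed by a full panel whenever it is abnormal, is a coherent design. This reading is possible. But the text does not say that confirmation repeats, and a separate, shorter list for subjects whose values are still above 3 × ULN points somewhat the other way. Sites could reasonably differ.

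A second reply is that the regular-assessments sentence ends at 3 × ULN, which suits subjects still dosing, so PT/INR is expected and only its interval is left open. That is fair, but an open interval is the point at issue.

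Third, there are other safeguards, and they limit the risk. A raised INR at confirmation would count as another laboratory finding and remove the allowance to continue. Bilirubin is checked every 2 weeks, and higher rising values are held. Section 8.3.2 also allows withdrawal on the Investigator's judgment. None of these schedules a later INR.

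A reader might also infer more than the documents support:

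- *An expected number of affected US subjects.* The interim subjects who stopped androgens at least 2 weeks before dosing (n = 113) include an unstated number who stopped between 2 weeks and 28 days and would now be barred, so the denominator is unknown. The share who improved or recovered while staying on drug (5 of 13) comes from a group of whom 12 are now barred.
- *A missed stop for eosinophilia.* Section 8.3.2 names it within the hepatitis symptoms ("right upper quadrant pain and tenderness, fever, rash, and/or eosinophilia"), so it is not clearly a stop on its own.
- *An inconsistency with the restart panel.* Closer testing after rechallenge is reasonable. The restart bullet matters here only as wording that can be reused.

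**Conclusion.** The point holds as a minor one. Following Section 12.2.2 as written can leave the INR arm of the 8.3.2 stop without a scheduled test while a subject continues dosing above 3 × ULN, most plausibly at a plateau of 3 to 5 × ULN. The possible delay is bounded by the next visit, on the Step 3 assumptions that the elevation is found at a visit, that it persists, that coagulation is tested at each visit, and that the Investigator orders no PT/INR in between. If the confirmation rule is meant to repeat at each result, the gap closes, but the protocol would need to say so.

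Few subjects are likely to be exposed, because the 28-day androgen rule removes most of the interim pattern. The documents give no case in which a late INR did harm, and they do not show that the stop rule is unworkable. This is a cheap safety improvement, not a major flaw.

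**What to change.** In Section 12.2.2, add PT/INR to the two-weekly list for subjects who continue dosing with ALT or AST above 3 × ULN, borrowing the wording of the restart bullet. A blood count for eosinophils could be added at the same time but is optional. With PT/INR on the list, the longest interval between required tests falls from about 165 days to 14.

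Two clarifications would help in the same edit: whether the regular-assessments sentence covers held subjects, continuing subjects or both, and whether the 72-hour confirmation applies once or at each result above 3 × ULN.

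The cost is one to three sentences in the next amendment. Both tests are already in Protocol Table 4 and blood is already drawn every 2 weeks, so the downside is a small added laboratory cost for a few subjects.
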